### 3.1 Schedule of Assessments

Baseline safety assessments may be made at the final designated visit of the prior TauRx study in which the subject was enrolled. For purposes of the open-label extension, these will be designated as Baseline (Visit 1, Day 1). If Visit 1 does not coincide with the final designated visit of the previous double-blind study of participation, medical history, concomitant medication use, and adverse events (AEs) should be updated; serum pregnancy testing should be performed in women of childbearing potential. If more than 42 days have elapsed since that final visit, additional baseline safety assessments must be repeated. The additional safety assessments include clinical laboratory testing (e.g., hematology and serum chemistry panels), vital signs (seated blood pressure and pulse, temperature, and respirations), body weight, targeted physical and neurological examinations (including an assessment for signs and symptoms of serotonin toxicity), and 12-lead Electrocardiogram (ECG). If needed to confirm eligibility or to evaluate an AE, unscheduled local 12-lead ECG testing and/or physical and neurological examinations may be performed if judged to be required by the investigator for any given subject. Baseline assessments may be repeated (also within 42 days) as determined by the new investigator for AD subjects transferring to a different site.

Safety assessments (described further in Section 7 of the TRx-237-020 protocol) will be repeated at each visit, i.e., approximately 2 weeks post-Baseline and at visits occurring approximately every 3 months (13 weeks) relative to Baseline (or upon early termination). These assessments include adverse event and concomitant medication recording, vital signs (seated blood pressure and pulse, temperature, and respirations), body weight, targeted physical and neurological examinations (including an assessment for signs and symptoms of serotonin toxicity), clinical laboratory testing (e.g., hematology and serum chemistry panels), and serum pregnancy testing in women of childbearing potential. A

12-lead ECG will be obtained in triplicate approximately every 6 months (or upon early termination).

The EuroQol – 5 Dimension – 5 Level (EQ-5D-5L) scale, applied to the subject and to the caregiver on behalf of the subject, will be evaluated at Baseline (as it is not used in the Phase 3 studies of prior participation). The Resource Utilization in Dementia – short version (RUD Lite) will be also be evaluated at Baseline if not available from within the prior 42 days. These evaluations will be repeated approximately every 6 months, i.e., approximately 26 and 52 weeks after Baseline.

The same 13-week schedule of in-clinic safety assessments will be maintained for continued treatment beyond the first 12 months (if there is re-consent approximately every 12 months), with no requirement for the Week 2 visit or Week 6 telephone contact in the second or any subsequent year of participation. Continued treatment will be restricted to those subjects for whom continued benefit is expected by the investigator to outweigh risk and informed consent is provided.

Additional targeted examinations may be performed as clinically indicated (e.g., in the event of an AE that requires such follow up or any reported change in the subject's physical condition).

Post-treatment safety assessments will be conducted at the follow-up visit to be scheduled to occur approximately 4 weeks after the last dose of study drug (End of Treatment or Early Termination). These visits should be scheduled for all subjects.

A schedule of assessments (the first 12 months of the study) is shown in Table 3-2.

Table 3-2: Schedule of Assessments (First 12 Months)

Visit Name	Baseline	First 12 Month Open-Label Extension					Follow-up
		2*	3	4	5	6 (End of Treatment or Early Termination)	
Overall Visit Number:	1	2*	3	4	5	6 (End of Treatment or Early Termination)	
Months Relative to Baseline Day:	--	--	3	6	9	12	13
Weeks Relative to Baseline Day:	--	2	13	26	39	52	56
(Allowable Time Window in days):	--	(±3)	(±14)	(±14)	(±14)	(±14)	(±14)
Informed Consent (Subject and Caregiver) (M)	X					X	
Inclusion/Exclusion Criteria Review (M)	X						
Concomitant Medication Recording/ Review (M)	X	X	X	X	X	X	X
Adverse Events / Medical History Review (M)	X	X	X	X	X	X	X
Study Drug Dispensing	X		X	X	X	X	
Study Drug Compliance Assessment		X	X	X	X	X	
Blood Samples for Laboratory Tests	X	X	X	X	X	X	X
Serum Pregnancy Test (women of childbearing potential)	X	X	X	X	X	X	X
Seated Blood Pressure and Pulse	X	X	X	X	X	X	X
Temperature and Respiratory Rate	X	X	X	X	X	X	X
Body Weight	X	X	X	X	X	X	X
ECG	X			X		X	X
Physical and Neurological Exam (including an assessment for signs and symptoms of serotonin toxicity)	X	X	X	X	X	X	X
MMSE (to inform the evaluation for possible serotonin toxicity)	X			X		X	X
RUD Lite	X			X		X	
EQ-5D-5L	X			X		X	

\*A documented telephone contact will occur between the scheduled Visit 2 and 3 study visits, scheduled to occur at approximately Week 6 (± 14 days) and will include AE and concomitant medication review.

Note: The same 13-week schedule of in-clinic safety assessments will be maintained for continued treatment beyond the first 12 months (if there is re-consent approximately every 12 months), with no requirement for the Week 2 visit in the second or any subsequent year of participation.

### **3.2 Assignment of Treatment**

This is not applicable to this open-label study as all subjects will receive LMTM.

Treatment assignment from the prior double-blind clinical study will be recorded in a listing.

Subjects will be assigned a study identification number with the first three digits for the study (020), the next two letters for the country, the next three digits for the site, and the last two digits for the sequential order of enrollment at a given site. These study identification numbers will be listed along with the subject's study identification number in the prior study. Subjects that have switched sites for this study will be flagged.

### **3.3 Study Treatment**

Study drug is provided as 100-mg tablets. The intended schedule of dosing is twice daily, with or without meals.

The initial LMTM dose for all subjects will be 200 mg/day, except for subjects from Study TRx-237-007 who were taking a reduced dose (i.e., 100 mg/day) and who should continue taking this reduced regimen upon entering this extension study. Thereafter, dosing will be flexible (in 100-mg decrements or increments). The dose may be increased (at Visit 3 or at any subsequent dispensing visit as determined by the investigator during the treatment period) or decreased (at any time at or after Visit 2) in response to benefit as judged by the investigator and safety and tolerability. The maximum allowable dose is 300 mg/day (or in those countries where limited by a CA or EC, 200 mg/day). The dose may also be interrupted at any time as needed (for up to 30 days at any one time). Study drug and regimens, including dose interruptions and modifications in response to adverse events, are further described in Section 6 of the TRx-237-020 protocol.

## **4. GENERAL ANALYSIS CONSIDERATIONS**

The Safety population will include all subjects who take at least one dose of study drug. All analyses described in this SAP will be based on the Safety Population. All subjects entering the study, even if not known to have taken a dose, will be accounted for in a listing.

The statistical analyses will be reported using summary tables, figures, and data listings. Continuous variables will be summarized with means, standard deviations, medians, minimums, and maximums. Categorical variables will be summarized by counts and by percentage of subjects in corresponding categories.

For purposes of calculations of change from baseline, Baseline (Visit 1) for the open-label study will be used. Depending on the parameter, the data may have been acquired during the double-blind study of prior participation.

Summary tables will present results by diagnosis (AD or bvFTD) and an “All Subjects” column.

Individual subject data obtained from the CRFs (including mapped data), central clinical laboratory (local laboratory results are entered on the CRFs), and any derived data will be presented by subject in data listings. Listings will include relative study day, where negative values will indicate visits prior to first dose of study drug in 020, and any data collected after discontinuation of study drug will be flagged as follow-up. All data captured on the CRF, including specific descriptions of ‘other’ and comments fields, will be included on the listings. Listings will be sorted by subject number.

All analyses and tabulations will be performed using SAS® Version 9.4 or higher. Tables, listings, and figures will be presented in RTF format. Upon completion, all SAS® programs will be validated by an independent programmer. In addition, all program output will undergo a senior level statistical review. The validation process will be used to confirm that statistically valid methods have been implemented and that all data manipulations and calculations are accurate. Checks will be made to ensure accuracy, consistency with this plan, consistency within tables, and consistency between tables and corresponding data listings. Upon completion of validation and quality review procedures, all documentation will be collected and filed by the project statistician or designee.

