A double-blind, placebo-controlled, Phase 2 study was also conducted (TRx-237-008), however, this study was terminated early for administrative reasons; 9 subjects were randomized. These subjects are also eligible for the open-label extension study.

The intent of this extension study is to provide LMTM treatment to those subjects in whom the benefit is judged to outweigh the risk, and to assess the longer-term safety and tolerability of LMTM given in doses of up to 300 mg/day, or in those countries where limited by a Competent Authority (CA) or Ethics Committee (EC), 200 mg/day. Treatment with LMTM in this study will either be *de novo* in subjects having been randomized to placebo or will be a continuation of treatment, albeit not necessarily at the same dose, to those subjects having been previously randomized to LMTM.

LMTM 150 mg/day is the lowest dose to which a subject participating in the Phase 2 or Phase 3 studies may be randomized. However, 200 mg/day has been chosen as the initial dose for continuation of treatment in this open-label extension study as it is intermediate to the doses previously used. This dose has been chosen because 250 mg/day was the active treatment in Study TRx-237-008 and is the active treatment for half of the subjects receiving LMTM in Study TRx-237-015, and 200 mg/day is the active treatment in Studies TRx-237-005 and TRx-237-007. Subjects previously randomized to placebo will receive LMTM for the first time at this dose. All subjects with AD will have undergone at least a 3-week period off-treatment prior to entry into this study; as prior treatment assignment will be blinded, this provides a standardized approach for treating all subjects. Dose interruptions are allowed at any time (to a maximum of 30 days on a given occasion) and dose adjustments are flexible to a minimum of 100 mg/day and a maximum of 300 mg/day (or 200 mg/day in those countries where limited by a CA or EC), to be based on safety and tolerability and benefit as judged by the investigator. As the acceptable risk/benefit balance will vary from subject to subject, the selection of dose is left to the discretion of the investigator, together with the subject and caregiver(s), based on judgment of the risk/benefit balance in any given subject.

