6.2.1 Initial Dose

The initial daily study drug regimen to which all subjects will be assigned is summarized in Table 6-2, including the number of tablets and LMTM doses.

Table 6-2 Initial Daily Study Drug Regimen: Tablets and LMTM Dose

Treatment	Tablet Contents (amount of MT)	Number of Tablets			Dose of MT		
		AM	PM	Daily Total	AM	PM	Daily Total
LMTM 200 mg/day	100 mg	1	1	2	100 mg	100 mg	200 mg

AM = morning; PM = evening

As the bvFTD subjects from Study TRx-237-007 are not required to return for a 4-week post-treatment visit prior to entering this open-label extension study, these subjects may choose to enroll in this extension study at Visit 9 of Study TRx-237-007 (*i.e.*, on the same day that they receive the last dose of study drug in the prior study). These subjects are to continue taking study drug (under the Study TRx-237-007 protocol) at the usual

designated time, and the first dose of study drug under this open-label extension study protocol will be instructed based on the last dose received under the prior study. Subjects from Study TRx-237-007 who are taking a reduced dose (*i.e.*, 100 mg/day) should continue taking this reduced regimen upon entering this extension study.

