7.1.3.1 Hemolytic Anemia

The subject should be evaluated at each visit for possible clinical symptoms associated with hemolytic anemia, in conjunction with review of hematology results. Should hemolytic anemia be suspected, follow-up testing should be performed as described in Section 7.3.2. The medical monitor should be contacted to discuss whether or not resumption of dosing is indicated or for any other questions.

The signs and symptoms of anemia include:

- Cyanosis, headache, anxiety, exercise intolerance, fatigue, confusion, dizziness, tachypnea, palpitation, dysrhythmia, seizures, and coma

Signs of possible hemolytic anemia include:

- Decrease by 20% from Baseline in RBC count and/or hemoglobin
- Abnormal RBCs in peripheral blood smear
- Elevation of reticulocyte count to above laboratory normal range
- Increase in LDH or indirect bilirubin, or low haptoglobin

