9.3.2 General Considerations

Results will be summarized descriptively; no inferential statistics are planned. Tabulations will be on the basis of all subjects pooled and also with subjects categorized separately by diagnosis and also by study of original participation. Data from the prior study will be mapped into the open-label database.

For purposes of calculations of change from baseline, Baseline (Visit 1) for the open-label study will be used. Depending on the parameter, the data may have been acquired during the double-blind study of prior participation.

For purposes of data tabulations, target visit windows will be assigned in the SAP.

Listings of by-subject data will be organized by subject number.

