23 APPENDICES

23.1 Appendix A: Assessments by Visit

Before participation in this extension study may begin, the subject and caregiver will each be provided with an information sheet and both will be given as much time as needed to decide whether or not to participate in this study. Subjects and caregivers must re-consent to continue participation annually (approximately Weeks 52, 104, *etc.*).

Baseline Visit (Visit 1, Day 1)

For potential subjects, the safety and efficacy assessments completed at the final designated visit of the prior TauRx study in which they were enrolled will serve as Baseline assessments for this extension study (unless otherwise noted). If the final visit occurred more than 42 days prior, assessments are to be repeated as specified below.

Subjects may continue participation at the same site at which they participated in the originating double-blind study or transfer to a geographically close investigational site (that also participated in the same study). Eligibility for continued open-label treatment is to be determined by the original investigator and, if applicable, a referral to a new site made. The new investigator will have access to the subject's prior study eCRFs and is to confirm eligibility. Baseline assessments may be repeated (also within 42 days) as determined by the new investigator for subjects transferring to a new site.

Screening / Baseline Assessments

The following assessments will be obtained, performed or measured at Baseline to confirm eligibility for enrollment prior to dosing or, in the case of the EQ-5D-5L, to provide a Baseline assessment (as this scale is not used in the prior double-blind studies):

- Written Informed Consent for participation in the study from the subject (or legally acceptable representative) and from the identified caregiver(s) (before any study related procedures may be performed)
- Inclusion and exclusion criteria review (to confirm eligibility)
- EQ-5D-5L (applied to the subject and to the caregiver on behalf of the subject)

In addition to the assessments listed above, the following assessments are to be performed if Baseline (Visit 1) does not coincide with the final designated visit in the prior double-blind study (Visit 11 in TRx-237-005, Visit 9 or Visit 10 in TRx-237-007, Visit 7 in TRx-237-008, or Visit 10 in TRx-237-015):

- Adverse events review (after signing of the Informed Consent)
- Medical history
- Prior and concomitant medication review

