## 4.2 Standard Calculations

Variables requiring calculation will be derived using the following formulas:

- **Baseline** - A baseline value, unless specified otherwise, is the last non-missing value recorded prior to the first dose of study drug in 020. If an assessment has the same date as the date of first dose of study drug in 020, the assessment will be counted as baseline (depending on the parameter, the data may have been acquired during the double-blind study of prior participation).
- **Study day** – For a given date (*date*), study day is calculated as days since the date of first dose of study drug in the open-label extension (*firstdose*):  
Study day =  $date - firstdose + 1$ , where  $date \geq firstdose$   
Study day =  $date - firstdose$ , where  $date < firstdose$
- **Days** – Durations, expressed in days, between one date (*date1*) and another later date (*date2*) are calculated using the following formula: duration in days =  $(date2 - date1 + 1)$ .
- **Weeks** – Durations, expressed in weeks, between one date (*date1*) and another later date (*date2*) are calculated using the following formula: duration in weeks =  $(date2 - date1 + 1) / 7$ .
- **Months** – Durations, expressed in months, between one date (*date1*) and another later date (*date2*) are calculated using the following formula: duration in months =  $(date2 - date1 + 1) / 30.4375$ .

- **Years** – Durations, expressed in years, between one date (*date1*) and another later date (*date2*) are calculated using the following formula: duration in years =  $(\text{date2} - \text{date1} + 1) / 365.25$ .
- **Body Mass Index (BMI)** -  $\text{BMI (kg/m}^2\text{)} = \text{weight (kg)} / [\text{height (cm)} / 100]^2$
- **Estimated Glomerular Filtration Rate (eGFR)** -  
 $\text{eGFR (mL/min/1.73 m}^2\text{)} = 175 \times (\text{serum creatinine in mg/dL})^{-1.154} \times (\text{Age in years})^{-0.203} \times (0.742 \text{ if female}) \times (1.212 \text{ if African American})$ .

Note that age on consent date is collected on the CRF and will not be calculated.

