## 7.2 Clinical Laboratory Evaluation

Central laboratory data are transferred electronically by Covance. The Data Transfer Specification document provides a detailed description of the content and format of the laboratory datasets. Both conventional and SI units are provided and will be summarized in separate tables and listings. The eGFR values will be calculated and included in the tables and listings for clinical chemistry parameters.

Results from local laboratories are entered into the CRF by the site; these will not be included in summary tabulations but will be included in the data listings together with the corresponding normal ranges. Values for local laboratory parameters will be converted to the corresponding alternative units, either conventional or SI, depending on how reported.

For the summary tabulations of laboratory results, Baseline is defined as the last non-missing value prior to first dose of study drug in 020. Laboratory tests obtained on the date of the first dose will be assigned to pre-treatment. For each analyte, Baseline values will be restricted to those subjects in the safety population for whom there is at least one post-Baseline value (either overall or for the corresponding target visit). Any lab result 14 or more days after the last dose will be considered post-treatment.

Visit windows are used when results are presented by target visit (see [Appendix A](#)). For each analyte, if a subject has multiple values within a visit window, the “worst” value as defined in [Appendix D](#) will be used for that visit window summary.

Results of all continuous laboratory parameters will be summarized using descriptive statistics at baseline and at each post-baseline target visit; the last available on-treatment value and post-treatment results will also be summarized. The baseline data may come from the prior study, if not repeated in 020. For each subsequent target visit, changes from baseline will also be summarized by the number and percentage of subjects and the mean, median, SD, minimum, and maximum values for continuous laboratory parameters. These will also be prepared for subjects categorized by diagnosis and AChEI/Memantine use.

Box and whisker plots will be presented for selected parameters including hemoglobin, reticulocytes (%), neutrophils, and liver function tests. Other parameters may be identified during data review.

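### The bvFTD laboratory, vital-sign and weight tables pool on-drug and off-drug Baselines because the SAP does not split them by prior treatment

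*SAP*

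**What the plan says.** SAP 4.2 defines Baseline as "the last non-missing value recorded prior to the first dose of study drug in 020". A value from the day of that dose counts, and it may come from the prior study. Protocol 9.3.2 also sets Visit 1 as the reference for change.

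Entry routes differ by diagnosis:

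- **bvFTD.** Under Protocol 6.2.1, "these subjects may choose to enroll in this extension study at Visit 9 of Study TRx-237-007", which is the day of the last dose in that study. Protocol Appendix A accepts "Visit 9 or Visit 10 in TRx-237-007" as the final designated visit. Laboratory tests, vital signs and weight are repeated only if more than 42 days have passed since that visit (Protocol 4.4 and Appendix A).
- **AD.** Protocol 2 states: "All subjects with AD will have undergone at least a 3-week period off-treatment prior to entry into this study".

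On tabulation, Protocol 9.3.2 plans pooled results and results "with subjects categorized separately by diagnosis and also by study of original participation". SAP 4 keeps only part of this: "Summary tables will present results by diagnosis (AD or bvFTD", plus All Subjects. For laboratory changes SAP 7.2 adds: "These will also be prepared for subjects categorized by diagnosis and AChEI/Memantine use". The shells for Tables 14.3.3.1.x to 14.3.3.3.x and 14.3.4.1.x have AD, bvFTD and All Subjects columns and repeats for non-users of AChEI/memantine. Prior study treatment appears only in selected adverse event tables (for example 14.3.2.1.3.3 and 14.3.2.2.3.3) and in listings. SAP 9 lists no change from the protocol and defers any to the study report.

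**The concern.** Change from Visit 1 means different things for different subjects in the bvFTD column. A subject on 200 mg/day for the 12 months of study 007 who enters at Visit 9 has any drug-induced shift already inside the Baseline. So does one who enters later, within 42 days, and whose Visit 9 values stand as Baseline. A former control subject starts from an off-active-dose value and can show the whole shift. A former active subject entering at Visit 10 starts about 4 weeks off drug. Averaging these groups pulls the mean change toward zero, and the reader cannot undo it from the tables.

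This matters because long-term safety is a primary objective and Protocol 4.7.8 names anaemia as a risk of the drug. Protocol 7.1.3.1 lists "Decrease by 20% from Baseline in RBC count and/or hemoglobin" as a sign of possible haemolytic anaemia. SAP Appendix B counts a 20% haemoglobin fall, and Appendix C counts weight changes of 7% and 10%, all against this Baseline.

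**Working it through.** The plan has no figure to reproduce: Protocol 9.2 gives no sample size and 9.3.2 plans no inference. What follows is illustrative arithmetic on a documented structure.

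**1. Which Baselines share a column**

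| Subject | Visit 1 value | Column |
|---|---|---|
| 007, active, Visit 9 entry or Visit 9 values carried forward | on drug | bvFTD |
| 007, active, Visit 10 entry | about 4 weeks off | bvFTD |
| 007, control | off active dose | bvFTD |
| 005, 008 or 015 | at least 3 weeks off | AD |

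The 3 weeks in the last row exceed the 14 days after which SAP 7.2 classes a laboratory value as post-treatment. The on/off mixture therefore lies within bvFTD and, through it, in All Subjects.

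**2. Mean change, bvFTD column.** Let f be the share previously on active drug and v the share of those with an on-drug Baseline. Assume the effect is at steady state (no further change in on-drug entrants) and the control is inert (the protocol calls it placebo; the SAP shells label it 8 mg/day). Then

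share of the off-to-on change retained = 1 − f × v.

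The documents give neither f nor v, so a range is shown:

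| f | v = 0.5 | v = 1.0 |
|---|---|---|
| 0.33 | 0.83 | 0.67 |
| 0.50 | 0.75 | 0.50 |
| 0.67 | 0.67 | 0.33 |

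**3. All Subjects.** With bvFTD share q and no residual effect in AD, retained = 1 − q × f × v. At f = 0.5 and v = 1:

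- q = 5%: 97.5%
- q = 10%: 95%
- q = 20%: 90%

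The values of q are also assumed.

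**4. Baseline-relative flags**

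- *Haemoglobin.* If it is already 10% down at Visit 1, a further 20% fall means 1 − 0.90 × 0.80 = 28% below the pre-drug value. If 15% down, 14.0 × 0.85 = 11.9 g/dL at Visit 1; the flag then needs 11.9 × 0.80 = 9.52 g/dL, a total fall of 1 − 9.52/14.0 = 32%.
- *Absolute cut-offs.* Appendix B also flags men at 11.5 g/dL or below and women at 9.5 g/dL or below. A man at 11.9 meets this after a further 0.4 g/dL, before he reaches 11.2 (20% below 14.0). For a woman, 9.5 lies just under 9.52, so the absolute rule adds nothing in this example.
- *Weight.* After an earlier 5% loss, the 7% criterion needs a total loss of 1 − 0.95 × 0.93 = 11.65%. The weight criteria have no absolute cut-off.

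The starting values and earlier losses are examples, not document figures.

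**The case against.** The strongest reply is that Visit 1 is the protocol's own Baseline and that SAP 1 limits safety reporting to study-emergent information. Measuring change since entry to the extension is legitimate, and an uncontrolled, descriptive study estimates no drug effect. This stands. The issue is how change from Visit 1 is tabulated, not the choice of Visit 1.

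Second, diagnosis columns already keep on-drug bvFTD Baselines apart from off-drug AD Baselines. That is right, and it confines the main problem to bvFTD.

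Third, other outputs help. Adverse events of special interest are shown by diagnosis and prior treatment, absolute values are summarised by visit, and listings exist. The absolute haemoglobin cut-offs protect men well in the example. None of these shows laboratory, vital-sign or weight change by prior treatment.

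Fourth, the Version 3.0 summary of changes sends some adverse event subgroup analyses to the Integrated Summary of Safety, which considers total exposure. It does not name laboratory or vital-sign changes as moved there.

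A reader might infer more than the documents support:

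- *AD changes are diluted by carry-over.* Nothing shows an effect persisting beyond 3 weeks off drug.
- *Restoring the by-study tabulation cures the bvFTD column.* Study 007 is its only source, so that column would not change.
- *A 20% red cell count fall is tabulated.* Appendix B has no red cell criterion; the sign in Protocol 7.1.3.1 is guidance to investigators.

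**Conclusion.** The point holds for the bvFTD column and, to a smaller degree, for All Subjects. The pooling follows directly from the Baseline rule, the entry routes and the table shells. Its size does not: 33% to 83% of the off-to-on change is retained if 33% to 67% were on active drug and 50% to 100% of those had an on-drug Visit 1, with a steady-state effect and an inert control. A reader might conclude that the bvFTD change is simply halved. That needs both a 1:1 split and every former active subject to enter on drug, whereas Visit 9 entry is optional.

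What is attenuated is a descriptive change and the Baseline-relative flags, not an estimate of drug effect. The weight flags are the least protected. Separately, the SAP omits the by-originating-study tabulation promised in Protocol 9.3.2 without recording the change. This is a worthwhile, cheap improvement to the tables; it does not invalidate the safety analysis.

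**What to change.** 1. In Tables 14.3.3.1.x, 14.3.3.2.x, 14.3.3.3.x and 14.3.4.1.x, add columns by prior study treatment within diagnosis, using the layout of Table 14.3.2.1.3.3.
2. Flag 007 subjects whose Baseline was taken on drug, whether by entry at Visit 9 or by Visit 9 values carried forward within 42 days.
3. Restore the tabulation by originating study from Protocol 9.3.2 in SAP 4, or record its removal with a reason in SAP 9. This separates the AD sources and keeps the SAP in line with the protocol.

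The cost is SAP wording and repeat table runs; prior treatment is already in Listing 16.2.1.1.1. The downside is more tables and small bvFTD cells.

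A second set of changes from the originating study's pre-dose baseline, for haemoglobin and weight, is optional. It costs more: SAP 4.1 limits mapped data to medical history, concomitant medication and adverse events, so a cross-study merge would be needed.
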